11.1.2. Recruitment for ART Cohort

- Trial participants newly diagnosed with acute or prevalent HIV infection in the intervention period (estimated at 75 total) and any partners of these individuals who are newly diagnosed through partner testing will be offered follow-up at the nearest KEMRI Research Clinic.
- At the research clinic, these individuals will be offered immediate ART (provided by NASCOP) to prevent secondary transmission and adverse health outcomes, with follow-up for 12 months.
- A separate consent (Consent 5) will be used for this follow-up. This consent will be reviewed at an intake appointment at the nearest KEMRI Research Clinic, so that newly diagnosed individuals have time to process their diagnosis and care options.
- If these individuals prefer not to participate in the KEMRI ART cohort, they will be
 offered referral. Several clinics offering HIV care, including ART, are available in the
 study area.
- Persons testing positive for HIV during the observation period will not be eligible for the ART cohort, but will be provided counseling and offered referral to any of several local care facilities.

11.1.3. Recruitment for APS Intervention

- All individuals newly diagnosed with HIV in the intervention period (both trial
 participants and partners) will be offered participation in the enhanced aPS
 intervention (i.e., aPS with testing for acute and prevalent HIV infection), using
 Consent 3. Newly diagnosed individuals can opt out of enhanced aPS and still be
 followed in the ART cohort, according to their preference.
- During the observation period, standard aPS (i.e., aPS with standard HIV testing)
 will be offered to newly diagnosed individual who have not yet informed their
 partners at the 6-week visit (detailed below).
- Counselors will make it clear that participation in the aPS intervention involves
 providing contact information about recent sexual partners. Individuals who are not
 willing to disclose partner information will be excluded from aPS.

11.1.4. Recruitment of Partners

Partners identified through the aPS intervention will be offered HIV testing
according to the period in which the associated index patient was diagnosed (i.e.,
standard rapid HIV tests in the observation period, testing for both acute and
prevalent HIV infection in the intervention period).

Version 1.1 17 July 2018 Page 30 of 137

- During the intervention period, partners who are newly diagnosed with HIV will be
 offered enrolment in the ART cohort at the nearest KEMRI Research Clinic and will
 also be offered participation in the enhanced aPS intervention.
- In this same period, partners who are uninfected and in an ongoing serodiscordant partnership will be offered enrolment in the PrEP cohort at the nearest KEMRI Research Clinic.
- Consent 4 will be used for enrolment of partners for standard HIV testing (observation period) or for the HIV-1 RNA testing intervention (intervention period).
- Consent 5 will be used for enrolment of partners into the ART cohort, and Consent 6 will be used for enrolment of partners into the PrEP cohort

11.1.5. Qualitative Interviews

- All individuals newly diagnosed with HIV in the intervention period (both trial
 participants and partners) and seronegative partners who enroll in the PrEP cohort
 described above will be offered participation in the qualitative interviews, using
 Consent 7. These individuals can opt out of the interviews and still be followed in
 the ART or PrEP cohort, according to their preference.
- During the observation period, individuals will not be recruited for interviews.

11.2. Stepped Wedge Trial

Figure 3 provides a flow diagram of procedures in the observation period and intervention period. The schedule of procedures for these visits is in Appendix 21.1 for the observation period and Appendix 21.2 for the intervention period.

11.2.1. Observation Period, Enrolment visit

- Consenting patients will take a brief computer-assisted self-interview or personal
 interview (CASI/CAPI) on a hand-held tablet computer. This survey will capture
 demographic information, onset of illness, and data on sexual behavior including
 partner numbers (with detailed questions on three most recent partners), relational
 timing (i.e., concurrent vs. sequential), transactional sex, and same-sex behavior.
 CASI/CAPI length will be monitored to ensure that the time required (target ≤20
 minutes) is not an undue burden on participants.
- After the CASI/CAPI, research staff will help patients who have a request form for PITC to find the laboratory. PITC results will be recorded, and facility staff will refer patients with a positive result to care as per their standard practice.
- At the conclusion of their study visit, participants will be asked about the last time they tested for HIV as well as the costs they incurred for the health facility visit.
- All study participants who are newly diagnosed with HIV at this visit will be asked
 for contact details in order to arrange a 6-week follow-up visit. Research staff will
 stress the importance of linking to care, the availability of ART regardless of CD4 cell
 count, and the need to inform partners that they should be tested.

11.2.2. Observation Period, 6-Week Follow-up Visit

 Individuals with a new diagnosis of HIV infection made in the observation period will be visited in person or seen to at the health facility from which they were recruited 6 weeks after diagnosis to repeat the CASI/CAPI and ascertain data on linkage to care, ART status, and partner notification outcomes. Linkage will be verified by demonstration of a clinic registration card, and ART status will be confirmed by demonstration of a regimen card and/or the patient's pills. Partner notification outcomes will be self-reported by the index patient.

- Participants who have not linked to care, started ART, or disclosed their HIV status will be offered counseling and referrals at this time.
- At the conclusion of this data collection and counseling, these index patients will be
 offered standard aPS. For those that accept, standard HIV rapid testing will be
 offered to all identified and successfully contacted partners.

Version 1.1 17 July 2018 Page 32 of 137

Observation Intervention Informed consent, enrolment Informed consent, enrolment CASI/CAPI survey CASI/CAPI survey Xpert® RNA testing, followed by PITC per Kenyan guidelines HIV rapid testing result result Exit study Exit study + result + result Newly diagnosed HIV Newly diagnosed HIV Linkage to care, Consent and enroll for Passive partner referral KEMRI ART Cohort Follow-up at 6 weeks for Consent and enroll for linkage and partner outcomes, enhanced aPS offering standard aPS if indicated APS = assisted partner services Follow-up at 6 weeks for linkage ART = antiretroviraltherapy and partner outcomes, CASI = computer-assisted self-interview regardless of uptake of ART CAPI = computer-assisted personal interview PITC = provider-initiated testing and counseling cohort and aPS components

Figure 3. Flow Diagram, Observation and Intervention Periods

Version 1.1 17 July 2018 Page 33 of 137

11.2.3. Intervention Period, Enrolment Visit

- After consent is obtained, research staff will draw a 4-mL blood sample from
 participants for intervention HIV testing, which will be conducted by a research
 laboratory technician in the facility laboratory or at the nearest KEMRI research
 laboratory.
 - For all participants, a sample of blood will be tested on-site or at the nearest KEMRI research laboratory for HIV-1 RNA using the *Xpert® HIV Qual* assay (Cepheid, Sunnyvale, California, USA). This assay has been found to be easy to use and feasible in a community-based facility with limited or no laboratory infrastructure [58].
 - For participants with HIV-1 RNA detected, rapid HIV tests will be conducted, to determine whether the participant has prevalent HIV (i.e., seropositive results) or acute HIV (i.e., seronegative or discordant results).
- During wait time for this testing (up to 90 minutes), participants will take the brief CASI/CAPI survey described above. After the CASI/CAPI, research staff will help patients who have a request form for lab tests other than HIV to find the laboratory. In any time remaining, a brief educational video on HIV will be shown.
- HIV test results will be provided in real-time, with post-test counseling by KEMRI research staff. Results will also be shared with the facility clinician.
- At the conclusion of their study visit, participants will be asked about the last time they tested for HIV as well as the costs they incurred for the health facility visit.
- All study participants who are diagnosed with acute or prevalent HIV infection by the KEMRI research team will be asked for contact details in order to arrange a 6week follow-up visit. ART cohort participation will also be offered at this time, and IPV assessment will be conducted to determine eligibility for the enhanced aPS intervention.
- Each health facility will work out a collaborative arrangement with KEMRI to ensure
 that these steps are fulfilled. There may be slight variations in the order of the above
 procedures, in order to ensure that patients and facility staff are minimally
 inconvenienced by the study.

11.2.4. Intervention Period, 6-Week Follow-up Visit

- Individuals with a new diagnosis of HIV infection made in the intervention period will be visited in person or seen at the KEMRI Research Clinic nearest to them 6 weeks after diagnosis to repeat the CASI/CAPI and ascertain data on linkage to care, ART status, and partner notification outcomes. Linkage will be verified by demonstration of a clinic registration card, and ART status will be confirmed by demonstration of a regimen card and/or the patient's pills. Partner notification outcomes will be self-reported by the index patient.
- Of note, additional data will be available on linkage, ART status, and partner notification outcomes for those participating in the enhanced aPS intervention and/or the ART cohort. However, the 6-week follow-up visit will serve to document

outcomes at the same time point in all trial participants, regardless of their uptake of other components of the Tambua Mapema Plus intervention.

11.3. ART Cohort for Newly Diagnosed Patients

- During the intervention period, all trial participants and partner participants with newly diagnosed acute or prevalent HIV infection will be offered referral to the nearest KEMRI Research Clinic, with study staff accompanying individuals to the Research Clinic if possible. At this site, these individuals will receive counselling about immediate ART initiation and partner notification (see below). The provision of immediate treatment, or TasP, to all newly diagnosed patients including those diagnosed with AHI has been approved by NASCOP and the Kilifi County Health Office.
- Medications will be provided at no cost through PEPFAR. Standard Kenyan first-line regimens will be used (currently tenofovir/lamivudine/efavirenz), with monitoring in accordance with Kenya MoH guidelines, continuing treatment indefinitely.
- Newly diagnosed persons who do not present to the research clinic within 3 days of their diagnosis will be contacted for a discussion of linkage to care at our research clinic or elsewhere if non-research options are preferred.
- Newly diagnosed patients enrolled at each KEMRI Research Clinic will be followed for 12 months at this site, with collection of data as follows for each visit:
 - Baseline visit
 - Confirmation of ART cohort eligibility and informed consent
 - Confirmation of contact details
 - Sociodemographic questionnaire
 - Risk assessment questionnaire
 - HIV testing to confirm status for seropositive patients and determine if seroconversion has occurred in AHI patients
 - IPV assessment
 - Risk reduction counseling
 - Mental health assessment
 - HIV cohort enrolment form
 - Medical history, including assessment for TB symptoms
 - Physical examination with collection of vaginal and/or rectal swabs as indicated for STI testing
 - Hepatitis B vaccine (if male-male sex or sex work reported)
 - ART counseling and initiation if prepared
 - Co-trimoxazole initiation
 - Isoniazid preventive therapy counseling and initiation if ART refused

- Urine collection for tests per ART Cohort Schedule (Appendix 21.4)
- Blood collection for tests per ART Cohort Schedule (Appendix 21.4), including plasma viral load to confirm AHI

Week 2

- Confirmation of contact details
- HIV testing to determine if seroconversion has occurred in AHI patients
- Risk reduction counseling
- Qualitative interview (if consents to this procedure)
- ART counseling, adherence assessment, and refills
- TB assessment, isoniazid counselling, and isoniazid preventive therapy if eligible
- Urine pregnancy testing if applicable and indicated
- o Months 1, 2, 4, 5, 7, 8, 10, 11
 - Confirmation of contact details
 - HIV testing to determine if seroconversion has occurred in AHI patients (months 1 and 2)
 - Risk reduction counseling
 - Hepatitis B vaccine dose 2 if indicated (month 1)
 - ART counseling, adherence assessment, and refills
 - TB assessment, isoniazid counselling, and isoniazid preventive therapy if eligible
 - Other medication refills as needed
 - Urine pregnancy testing if applicable and indicated

Week 6

- Confirmation of contact details
- IPV assessment
- Risk reduction counselling
- ART adherence counseling
- TB assessment, isoniazid counselling, and isoniazid preventive therapy if eligible
- Urine pregnancy testing if applicable and indicated
- o Months 3, 6, 9, and 12
 - Confirmation of contact details

- HIV testing to determine if seroconversion has occurred in AHI patients (months 3 and 6)
- Risk assessment questionnaire
- IPV assessment
- Risk reduction counseling
- Medical history, including assessment for TB symptoms
- Physical examination with collection of vaginal and/or rectal swabs as indicated for STI testing
- Qualitative interview (if consents to this procedure)
- Hepatitis B vaccine dose 3 if indicated (month 6)
- ART counseling, adherence assessment, and refills
- TB assessment, isoniazid counselling, and isoniazid preventive therapy if eligible
- Other medication refills as needed
- Urine pregnancy testing if applicable and indicated
- Urine collection from men for STI testing
- Additional at Months 6 and 12
 - Blood collection for tests per ART Cohort Schedule (Appendix 21.4)
 - Urine collection for urinalysis
- o Additional at Month 12
 - Repeat mental health assessment
- Interim visits may occur at any time during ART cohort follow-up. All interim
 contacts and visits will be documented in participants' study records and on
 applicable case report forms (CRFs).
- Mental health assessment at baseline will be conducted by CASI/CAPI, with results
 followed up by our counselors to ensure referral for mental health problems such as
 depression and problem drinking. Our counsellors and clinicians have been trained
 in motivational interviewing and working with peer navigators [59], and will
 encourage patients to take advantage of these services in support of their ART
 uptake and adherence.
- All ART cohort participants will undergo a repeat CASI/CAPI and collection of data on linkage, ART status, and partner outcomes at week 6, as described above. This 6week assessment will occur at the research clinic or at another location of the patient's choice.
- If a patient does not accept enrolment in the KEMRI ART Cohort, he or she will be
 offered referral to one of several large ART programs available in Mombasa,
 Mtwapa, or Kilifi. As described above, we will contact these individuals at week 6 to

Version 1.1 17 July 2018 Page 37 of 137

repeat the CASI/CAPI and collect data on linkage results, ART status, and partner outcomes.

11.4. Assisted Partner Services (aPS)

- 11.4.1. Observation Period Participants Diagnosed with HIV Infection (Index Cases)
 - Standard HIV care guidelines in Kenya recommend testing of partners of the index case through passive partner referral. Patients diagnosed with HIV infection during the observation period will be encouraged to refer their partners for this testing.
 - Partner outcomes will be self-reported by these patients at the 6-week follow-up visit, after which all observation period index patients will be offered standard aPS (with research staff, instead of index cases, contacting named partners), using procedures summarized in section 11.4.2. Partner outcomes among observation period participants who agree to provide names for standard aPS will be documented by study staff as described below. Of note, testing of partners of index patients diagnosed in the observation period will not include the Xpert® HIV Qual test, but will consist solely of standard HIV rapid tests conducted according to Kenyan National Guidelines.
- 11.4.2. Intervention Period Participants Diagnosed with HIV Infection (Index Cases)
 - During the intervention period, we will administer our enhanced aPS intervention to all consenting index patients on the day of diagnosis, either at the health facility where the case was diagnosed or at the nearest KEMRI Research Clinic, depending on the patient's preference.
 - Research staff will describe the rationale for providing aPS and procedures for
 having providers immediately notify partners without directly revealing the index
 patient's identity. Specifically, staff will indicate that index patients who wish to
 inform partners themselves will be allowed up to 3 days to do so, after which
 research staff will notify partners following the aPS procedures. In addition, if an
 index patient requests that a certain partner not be contacted, the research team will
 respect the patient's wish and only contact partners for whom the index patient has
 given permission.
 - We will use an assessment form adapted from [name] completed aPS study
 to identify and exclude any individual from aPS who is determined to be at high risk
 of IPV, defined as reporting IPV within the last 1 month. Of note, partner notification
 following these eligibility criteria in [name] completed trial at VCT sites in
 Kenya showed no difference in IPV in the control and intervention arms.
 - Staff will then ask whether the patient (if eligible) accepts aPS, and have the patient
 provide written informed consent for the aPS procedures, which include the
 collection of detailed information on the aPS participant's recent sexual partners.
 - Prior to initiating aPS interviews, research staff will explain that all information collected through the aPS process will be kept confidential, and reminded that staff will not reveal index cases' identities when contacting their partners.
 - Index patients who accept aPS will be interviewed using structured interview forms
 that will be used to obtain partner contacts and track partner outcomes.

- Research staff will use a timeline-follow back instrument to elucidate the number of
 unique sex partners that participants have had in the past 1 year for prevalent
 infection and the past 3 months for AHI. If any participant reports injection drug
 use, information about needle-sharing partners will also be elicited.
- For each identified sex partner, staff will collect information including demographic characteristics, contact information, case's relationship to the partner, case's sexual behavior with the partner, and case's knowledge of the partner's HIV status. All data will be collected using structured interview forms and recorded as numerical or categorical outcomes.
- Index cases will be assigned unique identification (ID) numbers and their partners
 will be assigned corresponding numbers that include a random prefix (to protect
 index case confidentiality) and an additional sequential number for each partner,
 allowing partners to be linked to index cases in our dataset.
- aPS intervention participants who are assessed as having a moderate risk for IPV, as
 described in section 13.3.3 under "Rating System for IPV" will undergo special
 monitoring after the aPS consent visit, as described in that section.

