- proportion with viral suppression (<1,000 copies/mL) by month 6 and month 12 following ART initiation.

Partner testing: For newly diagnosed individuals with acute or prevalent HIV, we will also compare the following week 6 outcomes between the observation and intervention periods:

- number of partners reported;
- number of partners successfully contacted;
- number of partners tested;
- number of partners newly diagnosed with prevalent HIV infection;
- number of partners newly diagnosed with AHI (0 in the observation period);
- number of HIV-infected partners newly engaged in care; and
- number of HIV-uninfected partners initiating PrEP.

For PrEP cohort participants (intervention period only) we will also assess:

- proportion initiating PrEP by month 3 following cohort enrollment;
- proportion with adherence >80%, measured by self-report or MEMS® cap at months 3 and 6 following PrEP initiation.

Impact and cost-effectiveness: Model outputs will include the following:

- HIV infections averted
- Deaths averted
- Disability-adjusted life-years (DALY) averted
- Costs per HIV infections averted
- Costs per death averted
- Costs per DALY averted

Impact and cost-effectiveness will be evaluated by comparing these outputs for standard care (observation period) to these outputs for the HIV-1 RNA testing intervention (intervention period).

Barriers and facilitators: Qualitative results will present barriers and facilitators to the following components:

- HIV testing uptake
- aPS uptake
- ART uptake
- ART adherence
- PrEP uptake
- PrEP adherence

Version 1.1 17 July 2018 Page 13 of 137

Novel HIV-1 RNA testing intervention to detect acute and prevalent HIV infection – Tambua Mapema Plus

Staff views: Qualitative results will present staff views on the detection of AHI and the research carried out at the HIV-1 RNA testing intervention facilities, including challenges to intervention scale-up.

Version 1.1 17 July 2018 Page 14 of 137

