6.3. Study Hypotheses

- Testing for prevalent and acute HIV infection (i.e. our HIV-1 RNA testing intervention) will increase rates of case-finding and linkage to care relative to standard PITC.
- aPS will identify additional cases of previously undiagnosed HIV infection, including small outbreaks in local sexual networks, with enhanced aPS using HIV-1 RNA testing identifying more infected partners than standard aPS using standard HIV rapid tests.
- Identification of previously undiagnosed acute and prevalent HIV infections will lead to
 a significant reduction in new HIV infections in Kenya and will be cost-effective under a
 range of assumptions.

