7.2. Secondary Objectives

- Linkage to care: To determine the feasibility, acceptability, and uptake of offering
 immediate linkage and treatment to all newly diagnosed HIV-infected patients in the
 intervention period, comparing this approach to standard care.
- Partner testing: To determine the feasibility, acceptability, and uptake of aPS for partner
 identification and testing, comparing enhanced aPS with HIV-1 RNA testing in the
 intervention period to passive referral followed by delayed aPS with standard HIV
 testing in the observation period.
- Impact and cost-effectiveness: To model the potential impact of the HIV-1 RNA testing, linkage, immediate treatment, and aPS interventions on the Kenyan HIV epidemic, in terms of incremental costs per HIV infection averted, death averted, and disability-adjusted life-year (DALY) averted, using data on standard care outcomes from the observation period and data on intervention outcomes from the intervention period.

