8. STUDY DESIGN

We will use a modified stepped wedge design to evaluate the yield of the HIV-1 RNA testing intervention at 6 public or private health facilities in Kenya, before (1,375 patients) and after (1,500 patients) intervention delivery. This study will be conducted in two phases at each site.

The first phase is the **observation period** in which all testing and treatment will be per Kenyan Ministry of Health guidelines and primary care clinician judgment. Adults seeking care at primary health care clinics who have never been diagnosed with HIV and have a risk score of 2 or higher will be offered participation. HIV testing will only be done if ordered by the primary care clinician. Research procedures in the observation period will consist of a CASI/CAPI at baseline (all participants) and a home visit at 6 weeks (only for those diagnosed with HIV at baseline). The 6-week visit will include a second CASI/CAPI and follow-up on uptake of care and treatment and partner notification. Those who have not yet notified partners will be offered assisted partner notification with standard HIV testing (i.e., standard aPS). Participants found to be HIV negative and those not tested will end their participation at the baseline visit. Those diagnosed HIV positive (estimated to be about 2%) will have 2 visits, baseline and 6 weeks.

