Opening of the observational phase at each site will be staggered in 3-month intervals so that no more than 2 sites will be in each phase at any given time. Each phase will last 3-6 months per site with the exception of the first site having only 3 months of observation to allow the study to

proceed more efficiently. Each site is anticipated to enroll approximately 125 participants per 3-month block for a total enrollment of 2875.

We expect to diagnose over two-fold more HIV infections through the HIV-1 RNA testing intervention than are currently diagnosed through PITC. Assisted partner notification should identify at least two-fold more previously undiagnosed individuals for each index case diagnosed than passive referral strategies (the current standard of care), augmenting intervention impact. We also expect that enhanced aPS will identify more previously undiagnosed individuals for each index case diagnosed than delayed standard aPS. Through modelling, we will estimate the impact of this combined intervention on HIV transmission (i.e., HIV infections averted) and clinical outcomes (i.e., deaths averted, DALYs averted) and evaluate the potential cost-effectiveness of this approach under a wide range of estimations. We expect this work to provide invaluable data that will help improve HIV testing and treatment as prevention in sSA.

Our HIV-1 RNA testing intervention network will include both private and public health facilities in a large, peri-urban area (population >100,000) in coastal Kenya (Figure 1). We will select six health facilities (2-4 public, 2-4 private) for inclusion in this study due to their size, central location (within 20 kilometers of one of our two KEMRI Research Clinics, located in Mtwapa and Kilifi), patient volume (>500 patients 18-39 years of age seen over 3 months), availability of HIV rapid testing on-site, availability of a private room for consenting participants, and willingness to collaborate with the research team. Four such facilities (2 private and 2 government) participated in AHI studies conducted by KEMRI in 2013 and 2014.

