15.3. Partner Testing

We will compare the following week 6 outcomes between the observation and intervention periods: (1) number of partners reported; (2) number of partners successfully contacted; (3) number of partners tested; (4) number of partners newly diagnosed with prevalent HIV

infection; (5) number of partners newly diagnosed with AHI (0 in the observation period); (6) number of HIV-infected partners newly engaged in care; (7) number of HIV-uninfected partners initiating PrEP. For PrEP cohort participants (intervention period only) we will also assess the proportion initiating PrEP by month 3 following cohort enrollment and the proportion with adherence >80%, measured by self-report or MEMS® cap at months 3 and 6 following PrEP initiation. The median, inter-quartile range, and range will be presented for each outcome in each period.

Outcomes will also be compared across study periods using Poisson GEE models with a small-sample variance correction [63]. Potential predictors, adjustment for confounding by calendar time, and interaction testing will be as described for the HIV-1 RNA testing intervention analysis above. We will also analyze local sexual network characteristics including the composition of individuals' personal sexual networks by attributes, relational type, relational timing, and relational duration. Characteristics will be compared for partners of index cases with AHI vs. prevalent HIV and for networks that include or do not include one or more AHI cases, using Pearson Chi square or Fisher exact tests for binary outcomes and non-parametric tests for continuous outcomes. We will also conduct a subset of these comparisons to the sexual networks of HIV-negative respondents provided through their CASI/CAPI data. Point estimates and standard errors for each behavioral parameter will be used to parametrize the modelling efforts described below. As above, in analyses in which multiple null hypotheses are tested, p values will be adjusted using the Holm–Bonferroni method.

15.4. Impact and Cost-Effectiveness

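### The week-6 partner comparison sets enhanced aPS against passive referral; the stated comparison with standard (delayed) aPS has no analysis

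*Combined protocol and SAP*

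**What the plan says.** **Time point.** For partner outcomes, the endpoint list in section 5 states that "we will also compare the following week 6 outcomes between the observation and intervention periods", and section 15.3 repeats it: "We will compare the following week 6 outcomes between the observation and intervention periods". The seven listed outcomes are to be compared by Poisson GEE. No later between-period time point is named.

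**When the observation period gets aPS.** Section 11.2.2 first collects linkage, ART and partner data at week 6, then says "At the conclusion of this data collection and counseling, these index patients will be" offered standard aPS. Section 11.4.1 gives the same order: partner outcomes are self-reported "at the 6-week follow-up visit, after which all observation period index patients will be offered standard aPS". It adds that staff will document partner outcomes for those who then name partners.

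**What is claimed.** Section 6.3 hypothesises "enhanced aPS using HIV-1 RNA testing identifying more infected partners than standard aPS using standard HIV rapid tests". Section 8 says: "We also expect that enhanced aPS will identify more previously undiagnosed individuals for each index case diagnosed than delayed standard aPS". Section 7.2 compares enhanced aPS in the "intervention period to passive referral followed by delayed aPS with standard HIV" testing. Section 8 also expects assisted notification to outperform passive referral.

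**Who is offered delayed aPS.** Section 11.4.1 offers it to all observation-period index cases. Section 8 is narrower: "Those who have not yet notified partners will be offered assisted partner notification with standard HIV testing". The summary table in section 5 and section 11.1.3 agree with section 8. Figure 3 and Appendix 21.1 attach undefined conditions to the offer.

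**The concern.** At week 6 no observation-period partner has yet been reached by standard aPS, so the observation arm of every partner comparison is passive referral. The comparison differs from the one in 6.3 in three ways at once: whether staff contact partners, when they do so, and which test partners receive. Only the third is the subject of 6.3 as worded.

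The risk is misattribution. Section 6.4.4 reports an earlier Kenyan trial of immediate aPS against aPS deferred for 6 weeks, with incidence rate ratios of 3.22 for partners testing positive, 3.78 for partners tested and 11.50 for new testers. Nothing in that account involves RNA testing of partners. A large week-6 ratio is thus expected from timing and access alone, yet under 6.3 it could be reported as RNA testing outperforming rapid testing.

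The outcomes in 15.3 do not separate the two. Item 4 counts partners with prevalent infection only, so detecting acute infection cannot raise it. Item 5 counts partners with acute infection, but its comparator is zero by design.

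**Working it through.** **Step 1: sequence.**

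| Event | Observation | Intervention |
|---|---|---|
| Diagnosis | Passive referral | Enhanced aPS offered |
| Week 6 | Partner outcomes recorded | Partner outcomes recorded |
| After week-6 data | Standard aPS offered | – |
| Later | Staff document outcomes; no analysis named | – |

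The week-6 estimand is enhanced aPS at diagnosis versus passive referral. Sections 15.1 to 15.4 specify nothing for the later row, and the five model scenarios in 15.4 do not include delayed standard aPS.

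**Step 2: the plan's nearest figure.** Section 14 gives limits of 39.8% to 56.3% for 48.0% of 150 partners. Exact (Clopper-Pearson) limits for 72/150 are 39.8% to 56.3%, so it reproduces. No power or precision is stated for any between-period partner comparison.

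**Step 3: expected HIV-positive partners.** Two sets of inputs.

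- *Set A*, from the earlier aPS trial in 6.4.4: 1.67 partners named per index case, 69% enrolled (taken as tested), 48% positive.
  - Observation: 0.02 × 1,375 = 27.5 index cases; × 1.67 × 0.69 × 0.48 = 15.2 positive.
  - Intervention: 75 × 1.67 × 0.69 × 0.48 = 41.5 positive.
- *Set B*, from section 14: 150 partners tested for 75 diagnoses, or two per index case. Extending this rate to the observation period is my assumption.
  - Observation: 27.5 × 2 × 0.48 = 26.4.
  - Intervention: 150 × 0.48 = 72.

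Both sets assume every observation index case is offered and accepts delayed aPS, Poisson counts, no overdispersion and no time adjustment. They also apply the 48% to previously undiagnosed partners, although 6.4.4 does not say whether it includes known positives.

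**Step 4: precision of enhanced versus delayed standard aPS.** If a share s of infected partners is acute, RNA testing multiplies diagnoses by 1/(1 − s). With s assumed to be 5% to 20%, the ratio is 1/0.95 = 1.05 to 1/0.80 = 1.25. SE(log ratio) = √(1/a + 1/b), where a and b are the positive partners in the two periods.

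- Set A: √(1/15.2 + 1/41.5) = 0.300.
- Set B: √(1/26.4 + 1/72) = 0.228.

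| True ratio | Set A: 95% CI, power | Set B: 95% CI, power |
|---|---|---|
| 1.05 | 0.58–1.89, 5% | 0.67–1.64, 6% |
| 1.25 | 0.69–2.25, 11.5% | 0.80–1.95, 17% |
| 2 (assumed, timing plus RNA) | 1.11–3.60, 64% | 1.28–3.12, 86% |

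If the offer is limited to index cases who have not notified partners, and 30% or 70% have already done so (assumed), Set A observation positives fall to 10.6 or 4.6. The interval for a true 1.25 then widens to 0.64–2.45 or 0.48–3.29.

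**Step 5: what can be estimated within the intervention period.** Acute share of newly diagnosed partners, exact 95% CI:

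- About 5%: 2/41 gives 0.6%–16.5%; 4/72 gives 1.5%–13.6%.
- About 20%: 8/41 gives 8.8%–34.9%; 14/72 gives 11.1%–30.5%.

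The 20% end matches section 14's 1% acute out of 5% diagnosed, in patients selected by a symptom score. Partners have no symptom criterion, so the lower end may be nearer.

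**The case against.** The strongest reply is that the week-6 contrast is deliberate. Section 8 and the first part of the 7.2 comparator ask for enhanced aPS against passive referral, and the design follows the immediate-versus-deferred trial in 6.4.4. Delayed-aPS outcomes are documented, the section 8 sentence is an expectation and not an endpoint, and item 5 of 15.3 already counts acute partners. All of this stands. It limits the point to a missing analysis and an over-reaching hypothesis.

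A reader might go further in three ways that the documents do not support.

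- *That the partner comparison is invalid, or that delayed-aPS data will be lacking.* It is a valid estimate of a different contrast, and 11.4.1 has staff record the delayed outcomes.
- *That enhanced versus delayed aPS could never be tested.* The low power applies to an RNA-sized effect. Set A is not a best case, and a combined timing-and-RNA ratio of 2 would have 64% to 86% power under the same optimistic model.
- *That the conflict over who is offered delayed aPS biases the week-6 result.* The offer comes after the week-6 data. The conflict matters for field practice and for the denominator of any delayed-aPS table.

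It would also be wrong to settle that conflict by tracing only partners who have not been told. Section 6.1 sets the aim of aPS as partners being notified, tested and referred, and a partner who was told may still be untested.

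**Conclusion.** The point holds. Every between-period partner comparison is enhanced aPS at diagnosis versus passive referral. The hypothesis in 6.3, the second expectation in section 8 and the delayed-aPS part of 7.2 have no analysis. The sequence of procedures settles this without any numerical assumption.

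The size of the gap does rest on assumptions. With an acute share of 5% to 20% among infected partners and the optimistic counts above, an RNA-specific ratio could be described but not usefully tested. The RNA contribution is best described within the intervention period.

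This affects a secondary objective and its hypothesis. The primary endpoints are untouched. The change should be made before results are written up, because its purpose is to prevent a misreading.

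**What to change.** 1. **Name the contrast.** In 15.3 and the section 5 endpoints, state that the week-6 comparison estimates enhanced aPS offered at diagnosis versus passive referral.
2. **Align the claims.** Reword 6.3 and the section 8 expectation to that contrast, and mark the delayed-aPS part of 7.2 as descriptive. Tabulate the delayed-aPS outcomes staff already document, per index case offered, over a fixed window (for example 6 weeks after the offer).
3. **One offer rule.** The investigators should choose a single rule and use it in section 5, section 8, 11.1.3, 11.2.2 (with Figure 3), 11.4.1 and Appendix 21.1. It should cover index cases who told only some partners, and should not bar tracing of partners told but not tested.
4. **Describe the RNA yield.** Among RNA-tested intervention-period partners, report acute cases over all newly diagnosed partners with an exact CI. Call it a gross yield: clinic-tested RNA-negative partners who do not enter the PrEP cohort get no rapid test, so RNA-negative seropositive infection among them is not seen. Home-tested partners (11.4.3) and PrEP-cohort enrollees (Appendix 21.5, footnote 1) do get one.
5. **Home testing.** Sections 11.4.3 and 12.1.3 give intervention-period partners the RNA test, but Appendix 21.3, footnote 2, mentions only rapid tests for those tested at home. Amend the footnote to say that their blood also goes for Xpert.

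**Cost.** Wording edits, one proportion and one descriptive table from data already collected; splitting acute cases into seronegative and discordant is a small extra tabulation. No added visit, form, consent or test. The trial gives up an RNA-versus-rapid aPS claim that the plan cannot support. The exact CI in item 4 ignores clustering of partners within index cases.
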